
PROPOSED INDICATIONS:
 
 • Treatment of chronic iron overload due to blood transfusions in patients 2 years of age and older when current chronic oral chelation therapy with other deferasirox products is inadequate. • Treatment of chronic iron overload in patients 10 years of age and older with non-transfusion-dependent thalassemia (NTDT) syndromes when current chronic oral chelation therapy with other deferasirox products is inadequate. 
PROPOSED RATIONALE: The efficacy of DST-0509 (deferasirox) tablets will be demonstrated in patients who were inadequately controlled on high doses of Jadenu® (“Jadenu”) or Exjade® (“Exjade”). Patients are defined as inadequate responders if their liver iron (Fe) concentration (LIC) is at least 5 mg Fe per gram of dry weight (Fe/g dw) and serum ferritin is >800 mcg/L, despite compliance with chronic chelation treatment.
	

OBJECTIVES:
 
Primary objectives:
 
 • This patient-pilot study will assess the safety, overall tolerability, and preliminary evidence DST-0509 tablets iron chelating activity compared to Jadenu or Exjade in patients with transfusion-dependent beta thalassemia (TDT), major or intermedia, or non-TDT (NTDT) patients with inadequate response to available deferasirox chelation therapy, defined as an LIC of at least 5 mg Fe/g dw and a serum ferritin >800 mcg/L. 
Secondary objectives:
 
 • To determine the single and multiple dose pharmacokinetic (PK) profile of total deferasirox (iron-bound and unbound) plasma concentrations during DST-0509 and Jadenu or Exjade treatments in fed TDT and NTDT patients. 	

POPULATION:
 
Adult patients (≥18 years) with TDT or NTDT and iron overload currently receiving iron chelation therapy (ICT) with Jadenu or Exjade and demonstrating inadequate response. Inadequate response is defined as serum ferritin levels that are persistently >800 mcg/L, determined by 2 separate assessments over the previous 2-4 weeks and not showing a decreasing trend over these weeks.
 
Patients should also have an LIC of >5 mg Fe/g dw measured by magnetic resonance imaging (MRI) in the 52 weeks prior to study entry and are receiving the maximal dose of oral commercial deferasirox (DFX), Jadenu: 28 mg/kg or Exjade: 40 mg/kg. Patients should be medication compliant in the opinion of the Investigator and willing to comply with treatment in the study.
	
STUDY DESIGN AND DURATION:	

This is a multi-center, open-label, two-period cross-over, patient-pilot study comparing DST-0509 to patient's prior ICT (Exjade or Jadenu) administered orally once daily (QD) for 28-days in each period, with a 7-day washout before the first treatment period, between treatment periods, and at the end of the study before patients recommence their prescription regimens (see Table 6-1). Patients will be randomized to one of two treatment sequences: DST-0509→Exjade/Jadenu or Exjade/Jadenu→DST-0509 (with subjects who were taking Exjade prior to study start receiving Exjade and those taking Jadenu at study start receiving Jadenu). This study is designed to assess the safety, tolerability, evidence of iron chelating activity, and PK profile of DST-0509 compared to Jadenu or Exjade in inadequately responding patients. Inadequate response to standard chelation therapy is defined based on the medical literature [6,7].

Up to 36 patients will be randomized 1:1 into one of two treatment sequences (study arms), of which up to 100% may be on Jadenu or Exjade at study entry, or a mix of the two. The planned randomization will assign up to 18 patients in each of two sequences: Sequence A: DST-0509 crossed to Exjade or Jadenu; Sequence B: Jadenu or Exjade crossed to DST-0509. The comparator treatment will be the patient's current chelation treatment. At the end of the study, patients previously on Jadenu or Exjade will revert to receiving their pre-study medication and dose following a 7-day washout period. A sufficient number of patients will be enrolled so there will be no need to replace study drop-outs. Study duration is approximately 14 weeks for each patient. A Study Flow Diagram is presented after this Synopsis (see Figure 3-1).

INCLUSION CRITERIA:

The following are the main inclusion criteria:

1. Written informed consent obtained prior to any study-related procedure being performed;
2. Patients at least 18 years of age or older at the time of consent;
3. Patient with TDT or NTDT syndromes and iron overload currently receiving iron chelation therapy with Jadenu or Exjade and demonstrating inadequate response assessed with serum ferritin and LIC;
4. Stable dosing with Jadenu or Exjade for >3 months prior to screening and receiving the maximal dose (Jadenu: 28 mg/kg or Exjade: 40 mg/kg);
5. Serum ferritin levels that are persistently >800 mcg/L determined by 2 separate assessments during screening over the previous 2-4 weeks prior to study treatment and not showing a decreasing trend over these weeks;
6. An LIC of >5 mg Fe/g dw measured by MRI in the 52 weeks prior to study entry;
7. Compliant with chelation therapy in the 3 months prior to enrollment as assessed by the Investigator:
 - Satisfaction with Iron Chelation Therapy (SICT) Quality of Life (QoL) composite score $\geq 60\%$, or determined by investigator that at least 75% of medication prescribed on a regular basis was taken (Investigator enquiry into patient prescription refill records, preferably 3 months if available); and
 - Willing to comply with chelation therapy for the duration of the study;
8. Agree not to use other anti-chelating agents concurrently;
9. Eastern Cooperative Oncology Group Performance Status (ECOG PS) of 0-1;
10. Women of childbearing potential (WOCBP) must use an adequate method of birth control (double barrier, e.g. hormonal control and barrier contraception) at least 28 days prior to the first administration of the study drug, during the study and for at least 30 days after the last dose of the study drug. (Section 7.5 for details);
11. Male patients whose partners are WOCBP must use an adequate method of birth control (double barrier control) at least 28 days prior to the first administration of the study drug, during the study and for at least 30 days after the last dose of the study drug; and
12. Patient is willing and able to comply with all protocol required visits and assessments.

EXCLUSION CRITERIA:

The following are the main exclusion criteria:

1. Patients with life expectancy less than 6 months;

2. Females of childbearing potential not on an adequate method of birth control, or who are pregnant or lactating;
3. History of non-compliance with chelation therapy (determined by the investigator, persistently taking less than 75% of prescribed dose in the 3 months prior to enrollment, or as determined by the Investigator based on medical history, SICT QoL overall score <60% or score in any SICT domain <50%).
4. Screening blood counts of the following:
 - a. Absolute neutrophil count < 1500/ μ L
 - b. Platelets < 100,000/ μ L
 - c. Hemoglobin < 8 g/dL; transfusion support is permitted;
5. Screening chemistry values of the following:
 - a. Alanine aminotransferase (ALT) and aspartate transaminase (AST) > 2.5 \times upper limit of the normal reference range (ULN)
 - b. Total bilirubin > 2 \times ULN
 - c. Creatinine > 1.5 \times ULN
 - d. Urine protein/creatinine ratio (UPCR) >0.5 mg/mg
 - e. Albumin < 2.8 g/dL;
6. History of congestive heart failure New York Heart Association (NYHA) class III or IV or uncontrolled hypertension at screening;
7. History of other malignancy within the previous 3 years, except basal cell or squamous cell carcinoma, or non-muscle invasive bladder cancer;
8. In the opinion of the Investigator, evidence of major inflammatory disease that would affect ferritin levels within 14 days prior to the start of study medication;
9. Major surgery within 30 days prior to the start of study medication;
10. Serious persistent infection within 14 days prior to the start of study medication;
11. Serious concurrent medical condition including central nervous system (CNS) disorders;
12. Requires concomitant treatment with systemic corticosteroids, or any other immunosuppressive agents, or has used such treatment in the past 10 days before study entry (use of prednisone or equivalent <10 mg/day orally or use of inhaled corticosteroids or topical steroids is permitted).
13. Previous history of difficulty swallowing oral medications;
14. Any condition that, in the opinion of the Investigator, would impair the patient's ability to comply with study procedures or study medication; or
15. Concomitant treatment with medications described in 7.4 "Prohibited Medications".

PATIENT WITHDRAWAL FROM STUDY:

Patients may be removed from the study for reasons including the following:

1. Significant protocol violation on the part of the Investigator or patient;
2. Significant noncompliance on the part of the patient as determined by the Investigator in consultation with the Medical Monitor;
3. Patient withdraws consent;
4. During the study, patient has the need for medications, supplements, ingredients and herbal therapies that are excluded (see [Section 7.4](#), "Prohibited Medications" for examples in each category; this list is not all inclusive);
5. Unacceptable toxicity based on laboratory or other clinical findings, based on Principal Investigator (PI) opinion;
6. Occurrence of any adverse event (AE) or condition that could, in the Investigator's opinion, interfere with the evaluation of the treatment effect or put the patient at undue risk;
7. Pregnancy; or

8. Other criteria, at the Investigator's discretion in consultation with the Medical Monitor.

DOSAGE FORMS AND ROUTE OF ADMINISTRATION:

DST-0509 will be supplied in 360 mg, 180 mg and 90 mg tablets. Jadenu is commercially available as tablets and Exjade as tablets for oral suspension and will be provided by the patient with their ongoing prescription. Dosing will be at equivalent (mg for mg) doses of DST-0509 or Jadenu. If converting from Exjade, the dose will be scaled for each treatment by 28 mg/40 mg (treatment/Exjade).

This is an open-label crossover study. Patients will receive Exjade or Jadenu at their previous stable dose. DST-0509 is taken with food, Jadenu is taken with or without a light meal, and Exjade is recommended to be taken without food. However, either Jadenu or Exjade can be administered according to the patient's previous regimen.

OUTCOME VARIABLES:

The primary outcome of the study will be the safety, overall tolerability, and preliminary evidence of DST-0509 iron chelating activity compared to Jadenu or Exjade.

Iron chelation

Serum ferritin will be assessed at screening (Visits 1 and 2) and on Days 1, 28, 36 and 63. Change from baseline in each treatment period will be assessed as the main efficacy variable for serum ferritin.

Efficacy responders, i.e., the proportion of patients who achieve serum ferritin <800 mcg/L, will be evaluated.

Pharmacokinetics

Trough deferasirox levels will be collected in the Screening period at approximately -4 and -2 weeks. Blood samples for PK analysis will be collected predose (-0.5 hour for trough level) and at 1, 2, 4, and 8 hours post dose on Days 1, 7, 28, 36, 42 and 63. The PK parameters of DST-0509 and Jadenu or Exjade will be derived from the concentration time data. The allowed sampling "window" is ± 15 min for the 1 and 2 hour time points, and ± 30 min for the 4 hour time point. For the 8 hour time point, the allowable window is ± 1 hour.

The goal of the PK analyses will be to characterize the PK of the inadequate responder population on their current DFX therapy at the end of 4 weeks compared to 4 weeks of therapy with DST-0509. The hypothesis is that a significant proportion of inadequate responders will have low exposures on current therapy compared to exposure with DST-0509.

Exploratory Pharmacogenomics

A blood sample will be taken at Visit 2 to collect germline DNA to allow for later exploratory sub-analyses of genotype vs exposures.

SAFETY AND TOLERABILITY ASSESSMENTS:

Exposure and safety parameters

At each clinic visit, treatment exposure will be estimated with compliance rates based on patient diary cards and pill counts, and tolerability will be assessed by general enquiry and specific iron chelation tolerability questions as well as by patient diaries concerning tolerability. Study patients will receive a diary to record gastrointestinal (GI) adverse events (AEs) of special interest (AESI) during the course of the study. Patients will be given the Bristol Stool Chart with diary and instructed on its use. All AE's will be monitored throughout the trial after the first dose.

Patient safety will be monitored per clinical standard of care including routine laboratory monitoring. This will include monthly CBC, chemistry panel, and urinalysis assessments. Urine will be collected to measure protein: creatinine ratio and serum CRP will be assessed.

Compliance

Patients will be responsible for supplying their own Jadenu or Exjade during the study. Pill counts will be performed at each visit in order to characterize patient compliance (calculated as % doses taken per protocol).

Additional measures of compliance will include Investigator enquiry into patient prescription refill records if available, satisfaction with iron chelation therapy (SICT) questionnaire [ref 8; [Appendix D](#)] and use of patient diaries.

Dose reductions

Dose reductions/interruptions of DST-0509 and Jadenu/Exjade are discouraged. However, in the event of a severe or higher AE lasting for 7 or more days, the PI, at their discretion, may reduce the dose by 25-33% or interrupt dosing. The maximum interruption allowable is seven days. Dose re-escalation is not permitted. When AE resolves or is mild, the patient may restart study from last dose visit per PI or Medical Monitor (MM) discretion.

Dose suspension

Dosing with either treatment should be suspended in event of significant cytopenia (platelet count <50,000/ml or ANC <1,500/ml). If cytopenia has not recovered to Grade 1 or less after suspension of treatment for 7 days, the patient will be withdrawn from the study.

STATISTICAL ANALYSES:

A comprehensive statistical analysis plan (SAP) will be written and approved prior to database lock for this study that describes the final analyses to be completed for safety, efficacy, and pharmacokinetic endpoints.

Data collected in this study will be presented using summary tables, figures, and patient data listings. Summary tables will present data by treatment group and by time of collection. Continuous variables will be summarized using descriptive statistics, specifically the number of patients (n), the mean, median, standard deviation, minimum and maximum, and coefficient of variations (%CV). Categorical variables will be summarized by frequencies and percentages. Confidence intervals will be provided where appropriate for derived endpoints. Figures will be used to support the presentation of certain data. Sensitivity analyses may be performed to examine the effect of missing data.

All confidence intervals (CIs), statistical tests, and resulting p values will be reported as 2-sided. Significance will be assessed at $\alpha = 0.05$ level and the significance level will not be adjusted for multiple comparisons in the exploratory efficacy endpoint analyses.

Four analysis populations are defined for this study as follows:

- Safety Population: All patients who received the planned study medication. The Safety Population will be used to assess safety and tolerability. Patients in the Safety Population will be analyzed with actual treatment.
- Intent-to-Treat (ITT) Population: The ITT population comprises all patients who received at least 1 dose of study medication and had at least 1 evaluable efficacy measurement after the first dose of DST-0509. Patients in the ITT population will be analyzed as randomized to treatment sequence.
- Per Protocol (PP) Population: The PP population comprises all randomized patients who completed the study according to all protocol requirements.
- PK Population: All patients who receive planned study medication and have sufficient post Baseline plasma samples obtained and assayed for drug concentration levels to allow for computation of PK parameters will be included in the PK Population. Patients will be included in the PK Population after review of the plasma concentration data. The rationale for inclusion or exclusion in the PK Population will be documented and listed.

Planned efficacy analyses will include examination of changes in iron chelation. Analysis by TDT and NTDT stratification will depend on recruitment status. Descriptive summaries of serum ferritin at each time point in each study period will be completed. Change from baseline in serum ferritin will be assessed with a mixed model for repeated measures (MMRM) to assess changes within each treatment period and time. Categorical summaries will be presented for efficacy responders, i.e., the proportion of patients who achieve serum ferritin <800 mcg/L.

Pharmacokinetic parameters will be derived using model-independent methods (non-compartmental analysis: NCA) as implemented in Phoenix 7, WinNonlin (version 7.1) and will be based on DST-0509 and Jadenu plasma concentrations from patients in the PK Population.

Pharmacokinetic parameter estimates will be estimated for each treatment. Both single dose PK parameter estimates (following the first dose in a treatment sequence) and multiple dose pharmacokinetic parameter estimates will be completed to characterize DST-0509 and Jadenu. Other pharmacokinetic parameters may be defined as data are explored in the Phase 2 study.

Safety analyses will be performed on the Safety Population. AEs will be coded using the Medical Dictionary for Regulatory Activities (MedDRA) dictionary (version 20.1). Incidences (number and percent) of Treatment Emergent AEs (TEAEs), those events that started after dosing or worsened in severity after dosing, will be presented by treatment group. Incidences of TEAEs will also be presented by maximum severity and relationship to study medication. Laboratory data and vital sign information will be summarized by treatment group as summary statistics for value and change from Baseline at each individual time point. Summary statistics will include n, mean, median, standard deviation (SD), minimum, and maximum. Details for the additional safety endpoints will be provided in the SAP.

SAMPLE SIZE DETERMINATION:

The primary endpoints in this patient-pilot study are safety and tolerability with special interest in gastrointestinal AEs such as diarrhea. Evidence of DST-0509 iron chelating activity is also of special interest but is considered preliminary for this study and will not be considered in sample size estimations. If the underlying true probability of a diarrhea AE is 12% (Jadenu label 2015[2]), then there will be a 98% probability of observing at least one event in this study with a total sample size of 30 subjects. The table below presents a range of diarrhea AE rates provided from Jadenu clinical trials and the probability of observing at least 1 or 2 for our planned sample size. Given the same adverse event rate for diarrhea, there will be an 89% probability of observing at least two events in this study.

Underlying Event Rate	Probability of Observing at Least 1 Diarrhea AE		
	N=24	N=30	N=36
9%	0.90	0.94	0.97
12%	0.95	0.98	0.99
21%	>0.99	>0.99	>0.99

Underlying Event Rate	Probability of Observing at Least 2 Diarrhea Events		
	N=24	N=30	N=36
9%	0.65	0.77	0.85
12%	0.80	0.89	0.94
21%	0.97	0.99	>0.99

It is expected that most reasonably common AEs will be observed in this small study and will provide information for future studies.

SITES:

[figure not shown]
To be determined

SPONSOR:

DisperSol Technologies, LLC

STUDY FLOW DIAGRAM

Treatment A (28 days) = DST-0509
Treatment B (28 days) = Jadenu/Exjade¹

*Up to 36 patients are planned.

- Subjects taking Exjade prior to study start will receive Exjade (treatment B) in the assigned Period 1 or cross-over Period 2. Those patients taking Jadenu prior to study start will receive Jadenu (treatment B) in the assigned Period 1 or cross-over Period 2. Dosing will be at equivalent (mg for mg) doses of DST-0509 for Jadenu. If crossing over from Exjade to DST-0509, or vice versa, the dose will be scaled to 28 mg/40 mg (DST-0509/Exjade).
- For all patients entering the trial, a 7-day washout is required.
- Visit 11 will be a phone call from study staff to the patient. The phone call will confirm that the patient has conducted the 7-day washout period before recommencing prior iron chelation therapy. AEs and concomitant medications will also be collected by phone on Visit 11.

SCHEDULE OF PROCEDURES

Period	Screening	Eligibility	7-day Washout ¹	Period 1 Treatment (DST-0509 or Jadenu/Exjade)				7-day Washout	Period 2 Treatment (Jadenu/Exjade or DST-0509)				7-day Washout ¹¹ and Follow-up
				3	4	5	6		7	8	9	10/ET	
Visit	1	2											
Day	-28 to -15	-14 to -8	-7 to -1	1	7	14	28	29-35	36	42	49	63	70
Window (days)					±1	±1	±1		±1	±1	±1	±1	±1
Informed Consent	X												
Medical and Surgical History	X												
Prior Medications	X												
Body weight and Height	X												
Washout Instructions ²		X					X					X	
Eligibility Review	X	X		X									
Randomization				X									
Dispense Investigational Product ³				X					X				
Safety													
Vital signs ⁴	X			X		X	X		X		X	X	
Physical Examination ⁵	X			X		X	X		X		X	X	
Electrocardiogram (ECG)				X					X				
Chemistry, Hematology (CBC) and Urinalysis ⁶	X			X		X	X		X		X	X	
Serum CRP	X	X		X			X		X			X	
Urine Pregnancy Test ⁷	X												
Urine for Protein:Creatinine	X			X		X	X		X		X	X	
ECOG PS (Appendix C)	X			X			X		X			X	
Adverse Events				X	X	X	X		X	X	X	X	X
Concomitant Medications	X			X	X	X	X		X	X	X	X	X
Dispense gastrointestinal AESI diary and Bristol Stool Chart	X			X					X				

Period	Screening	Eligibility	7-day Washout ¹	Period 1 Treatment (DST-0509 or Jadenu/Exjade)				7-day Washout	Period 2 Treatment (Jadenu/Exjade or DST-0509)				7-day Washout ¹¹ and Follow-up
				3	4	5	6		7	8	9	10/ET	
Visit	1	2		3	4	5	6		7	8	9	10/ET	11
Day	-28 to -15	-14 to -8	-7 to -1	1	7	14	28	29-35	36	42	49	63	70
Window (days)					±1	±1	±1		±1	±1	±1	±1	±1
and diary													
Review gastrointestinal AESI diary		X		X	X	X	X		X	X	X	X	
Review Bristol Stool Chart diary		X		X	X	X	X		X	X	X	X	
Collect gastrointestinal AESI diary				X			X					X	
Collect Bristol Stool Chart diary				X			X					X	
Treatment Compliance ⁸				X	X	X	X		X	X	X	X	
Administer SICT questionnaire ⁸		X											
Efficacy Assessments													
Ferritin monitoring	X	X		X			X		X			X	
Pharmacogenetic monitoring		X											
Pharmacokinetics													
Trough sampling ⁹	X	X											
Pharmacokinetic sampling ⁹				X	X		X		X	X		X	
Next Visit Instructions ¹⁰				X	X	X	X		X	X	X		

Abbreviations AESI = adverse events of special interest; CBC = complete blood count; CRP = C-reactive protein; ECOG PS = Eastern Cooperative Oncology Group Performance Status; SICT = satisfaction with iron chelating therapy; ET = Early Termination.

1. Instructions for washout provided at Eligibility visit (Visit 2).
2. For patients on iron chelation therapy prior to randomization, and for washout for all patients between periods and after last treatment.
3. DST-0509 will be supplied in 360 mg, 180 mg and 90 mg tablets. Patients will receive Jadenu or Exjade at their previous stable dose. All treatments will be administered daily orally with food in the morning. Dosing will be at equivalent (mg for mg) doses of DST-0509 for Jadenu. If crossing over from Exjade to DST-0509, or vice versa, the dose will be scaled to 28 mg/40 mg (DST-0509/Exjade).
4. Vital signs will include the measurement of blood pressure, heart rate, respiratory rate and body temperature.
5. A full physical examination will be performed at Screening, Day 28 and Day 63. A brief physical examination will be performed on Day 1, 14, 36, and 49.

6. Chemistry, Hematology (CBC) and Urinalysis measurements are described in Section [7.11.1](#).
7. Urine Pregnancy Test will be performed for women of childbearing potential.
8. At clinic visits, dosing will be observed by site staff. Initial and returned pill counts will be used to calculate compliance (% doses taken per protocol). Additional measures of compliance will include Investigator enquiry into patient prescription refill records if available, satisfaction with iron chelation therapy (SICT) questionnaire [ref 8; [Appendix D](#)] and use of patient diaries.
9. A trough sample will be collected at Visit 1 and Visit 2. Blood samples for pharmacokinetic sampling will be drawn predose (-0.5 hour for trough levels) and at 1, 2, 4, and 8 hours post dose on Days 1, 7, 28, 36, 42 and 63. The allowed sampling “window” is ± 15 min before 4 hours and ± 30 min at 4 hours respectively. For the 8-hour time point the allowable sampling window is ± 1 hour. A 7-day washout period will occur at the end of study on Day 63; completion confirmed by a follow-up phone call on Day 71 to inquire on adverse events and concomitant medications.
10. Patients are instructed not take their medication before they arrive for their next visit.
11. A 7-day washout period will occur at the end of study on Day 63; completion confirmed by a follow-up phone call on Day 70 to inquire on adverse events and concomitant medications.

TABLE OF CONTENTS

PRINCIPAL INVESTIGATOR SIGNATURE SHEET	2
SPONSOR SIGNATURE SHEET	3
PROTOCOL SYNOPSIS	5
TABLE OF CONTENTS.....	15
LIST OF ABBREVIATIONS AND DEFINITION OF TERMS.....	20
1. INTRODUCTION.....	23
1.1 Background.....	23
1.2 Clinical Studies.....	24
2 OBJECTIVES	27
2.1 Primary	27
2.2 Secondary	27
3 INVESTIGATIONAL PLAN	28
3.1 Overall Study Design	28
3.2 Discussion of Study Design.....	30

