8.5 Statistical Analyses

A comprehensive statistical analysis plan (SAP) will be written and approved prior to database lock for this study that describes the final analyses to be completed for safety, efficacy, and pharmacokinetic endpoints.

Data collected in this study will be presented using summary tables, figures, and patient data listings. Summary tables will present data by treatment group and by time of collection. Continuous variables will be summarized using descriptive statistics, specifically the number of patients (n), the mean, median, standard deviation, minimum and maximum, and coefficient of variations (%CV). Categorical variables will be summarized by frequencies and percentages. Confidence intervals will be provided where appropriate for derived endpoints. Figures will be used to support the presentation of certain data. Sensitivity analyses may be performed to examine the effect of missing data.

All confidence intervals (CIs), statistical tests, and resulting p values will be reported as 2-sided. Significance will be assessed at $\alpha = 0.05$ level and the significance level will not be adjusted for multiple comparisons in the exploratory efficacy endpoint analyses.

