MRT	Mean residence time based on concentration-time data extrapolated to infinity, computed as $AUMC_{(0-\infty)} / AUC_{(0-\infty)}$
Multiple dose pharmacokinetic parameters within each sequence:	
Tau	The (assumed equal) dosing interval for steady-state data.
T_{max}	Time of maximum concentration sampled during a dosing interval.
T_{min}	Time of minimum concentration sampled during a dosing interval.
C_{min}	Minimum concentration between dose time and dose time + Tau (at T_{min}).
C_{avg}	Average concentration over the dosing interval, computed as AUC_{0-tau}/tau .
%_Fluctuation	$100 \cdot (C_{max} - C_{min}) / C_{avg}$, for C_{min} and C_{max} between dose time and Tau.
Cl_{ss}/F	An estimate of apparent oral clearance after multiple dosing, computed as Dose/ AUC_{0-tau} .
C_{max}	Maximum concentration between dose time and dose time + Tau (at T_{max}).
AUC_{0-tau}	Area Under the Plasma Concentration curve from the time of the dose to the end of the dosing interval.

Additional PK parameters may be derived as need to characterize both single dose and multiple dose PK profiles.

All reported sampling time deviations will be taken into consideration for evaluation of PK parameters. In the case where concentrations of study medications cannot be determined due to bioanalytical or clinical reasons; these values will be set to missing for the statistical and pharmacokinetic analysis.

The main absorption and disposition parameters will be estimated using a non-compartmental approach with a log-linear terminal phase assumption. The trapezoidal rule will be used to estimate the area under the curve (linear trapezoidal linear interpolation) and the terminal phase will be estimated by maximizing the coefficient of determination estimated from the log-linear regression model. However, disposition parameters may be estimated for individual concentration-time profiles on Day 1 where the terminal log-linear phase cannot be reliably characterized. Descriptive statistics will be calculated for plasma concentrations at each individual time point and for all pharmacokinetic parameters. The individual plasma concentration/time profiles will be presented using the actual sampling times whereas the mean plasma concentration/time profiles will be presented using the theoretical sampling times.

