8.5.4.2 Statistical Analysis

Statistical analyses will be generated using SAS (version 9.0 or higher) for the Mixed procedure. The natural logarithmic transformation of PK parameters as well as the rank-transformation of T_{max} will be used for all statistical inference. Subjects who do not have parameters for both DST-0509/Jadenu or DST-0509/Exjade treatments will not be included in the respective statistical bioequivalent analyses.

Exposure pharmacokinetic parameters (C_{max} , AUC) will be statistically analyzed using an Analysis of Variance (ANOVA) model. The fixed factors included in this model will be the treatment received, the period at which it was given as well as the sequence in which each treatment is received. A random factor will also be added for the patient effect (nested within sequence).

The 90% confidence interval for the exponential of the difference in LS means between Treatments will be computed. If there are sufficient data for both Jadenu and Exjade, both will serve as reference in the respective analysis, no pooling of data between the reference treatments (Jadenu, Exjade) will be performed.

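### The synopsis states the PK hypothesis as a proportion of patients with low exposure, but the only inferential exposure comparison fixed in Section 8.5.4.2 is a mean ratio, which does not determine that proportion

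*Protocol*

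**What the plan says.** The Pharmacokinetics paragraph under Outcome Variables in the protocol synopsis gives a goal and then a hypothesis. The goal is descriptive: "The goal of the PK analyses will be to characterize the PK of the inadequate responder population on their current DFX therapy", taken at the end of 4 weeks and set against 4 weeks of DST-0509. The hypothesis is that "a significant proportion of inadequate responders will have low exposures on current therapy compared to exposure with DST-0509".

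Section 8.5.4.2 then sets the comparison. Cmax and AUC, log-transformed, "will be statistically analyzed using an Analysis of Variance (ANOVA) model" with treatment, period and sequence as fixed factors and patient within sequence as a random factor. The result is stated as follows: "The 90% confidence interval for the exponential of the difference in LS means between Treatments will be computed". If both comparators have enough data, each is its own reference and "no pooling of data between the reference treatments (Jadenu, Exjade) will be performed".

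Section 8.5.4.1 adds output without inference: "Descriptive statistics will be calculated for plasma concentrations at each individual time point and for all pharmacokinetic parameters". Individual concentration-time profiles are also to be presented.

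The secondary objective (Section 2.2) is to determine the single- and multiple-dose PK profile. Section 8 leaves complete details to the SAP and says that it summarises the key aspects.

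**The concern.** The hypothesis is about how many patients are low, each judged against that patient's own exposure on DST-0509. The fixed comparison is about the average patient. The two differ when benefit is concentrated in a subgroup, which is the product rationale in Section 1.1: better bioavailability where poor bioavailability has limited the drug's effect.

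As written, every PK analysis named in Section 8.5.4 can be completed without producing the quantity that the hypothesis names. A count added later, with its cut-off chosen after open-label data have been seen, would be hard to interpret, because ordinary day-to-day variation alone puts a sizeable share of patients below any plausible cut-off.

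**Working it through.** **The plan's own figure.** The protocol gives no figure for the PK hypothesis. Its only sample-size figures are for diarrhea (Section 8.1: 12% rate, N = 30). They reproduce: 1 − 0.88^30 = 0.978 for at least one event, and 0.978 − 30 × 0.12 × 0.88^29 = 0.890 for at least two. They do not bear on this point.

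**Inputs.** N is up to 36 (Section 3.1). There is one end-of-treatment profile per period, Days 28 and 63, and one earlier repeat-dose profile, Days 7 and 42 (Section 7.11.2). The protocol gives no cut-off, within-patient CV or expected ratio. The values used below are assumptions.

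**1. Does the mean ratio fix the proportion?** Let R be a patient's true DST-0509:comparator ratio. The geometric mean is the exponential of the mean of ln R.

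- Every patient at R = 1.30: geometric mean 1.30.
- 30% at R = 2.4 and 70% at R = 1.0: exp(0.3 × ln 2.4) = exp(0.263) = 1.30.

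The corresponding comparator:DST-0509 ratios are 1/1.30 = 0.77 in the first case, and 1/2.4 = 0.42 or 1.0 in the second. With a cut-off of 0.8, 100% of patients are low in the first case and 30% in the second.

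A smooth distribution gives the same message. With a geometric mean of 1.25 and a log-normal R of CV c, the share with comparator exposure below two thirds of DST-0509 exposure is Φ((ln 1.25 − ln 1.5)/s), where s = √ln(1 + c²). For CVs of 20, 40, 60 and 80% the share is 18, 32, 37 and 40%.

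**2. Would the planned interval reveal the subgroup?** The 30/70 mixture adds an SD of ln 2.4 × √(0.3 × 0.7) = 0.875 × 0.458 = 0.40 to the within-patient log ratio. At a within-patient CV of 30%, noise alone gives √(2 × ln 1.09) = 0.415. Together they give √(0.415² + 0.401²) = 0.577. With N = 36, one comparator and t(0.95; 34) = 1.691, the 90% CI around 1.30 is:

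- without subgroup: half-width 1.691 × 0.415/6 = 0.117 on the log scale, giving 1.16 to 1.46;
- with subgroup: half-width 1.691 × 0.577/6 = 0.163, giving 1.10 to 1.53.

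The interval widens, but a higher day-to-day CV widens it too: at 40% with no subgroup it is 1.11 to 1.52. The interval alone therefore does not identify the subgroup.

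**3. How noisy is a simple count?** With no true difference, P(observed ratio < 0.8) = Φ(ln 0.8/(√(2/k) × √ln(1 + CV²))), where k is the number of profile days averaged per period.

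| Within-patient CV | k = 1 | k = 2 |
|---|---|---|
| 20% | 21% | 13% |
| 30% | 30% | 22% |
| 40% | 34% | 28% |

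**4. Precision of a reported proportion.** Exact 95% intervals for one third of patients low are 16–55% (8/24), 17–53% (10/30) and 19–51% (12/36). If 36 patients split evenly between Jadenu and Exjade, 6/18 gives 13–59%.

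**The case against.** The strongest reply is that this belongs in the SAP. The protocol defers complete PK details there, nothing in Section 8.5.4.2 forbids a per-patient summary, and a cut-off is the kind of item a SAP supplies. The hypothesis appears once, in the synopsis, directly after a descriptive goal. Section 2.2 is descriptive and the sample size uses no PK quantity. Individual profiles, listings and SDs are planned, so a 30% subgroup at 2.4-fold could be visible to someone who looks.

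Much of this stands and limits the point. A reader might infer that the trial fails a formal test of its PK hypothesis. The documents set no such test, and the sentence can be read as motivation for a pilot. A reader might also infer that the planned output would hide a subgroup altogether. It would not: the mean ratio is unchanged, but the interval widens and the individual data are shown. Nor can one say that the plan refuses to use the repeated profile days, since Section 8.5.4.2 does not state which days enter the model.

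A full patient-by-treatment random-effects model over both days in each period is not clearly better. A Gaussian term does not fit a two-group mixture, its variance would be poorly estimated within each comparator, and Days 7 and 42 lie outside the stated end-of-4-weeks target.

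What the reply does not remove is that the protocol goes beyond silence. It fixes transformation, factors, interval level and handling of references for a quantity other than the one in its hypothesis. For ferritin it does the opposite, giving a responder cut-off and a categorical summary.

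**Conclusion.** The point holds as a mismatch between a synopsis hypothesis about a proportion and a Section 8.5.4.2 comparison of means. The same mean ratio of 1.30 is compatible with 30% or 100% of patients low at a cut-off of 0.8. This shows that the mean ratio does not determine the proportion; it does not predict what the trial will find. The cut-offs, CVs and mixture are assumptions because the protocol supplies none. The data needed are already being collected, so the gap lies in the missing definition and summary. The matter concerns a secondary, descriptive part of a pilot. It should be corrected, but it does not affect the primary objectives.

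**What to change.** Choose one of two changes before database lock.

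1. **Keep the hypothesis.** In Section 8.5.4.2, define low exposure as a within-patient comparator:DST-0509 ratio of a named steady-state exposure parameter at the end of 4 weeks (Day 28 against Day 63, direction set by sequence) below a stated cut-off. Report the proportion below it with an exact 95% CI, separately for Jadenu and Exjade, beside the mean ratio. Label it descriptive and imprecise. Use the Day 7 and Day 42 profiles only as a supportive gauge of day-to-day variability, so that the proportion can be read against the 21–34% that noise alone could produce from one day per period under the assumed CVs.

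2. **Reword the hypothesis.** State it in the synopsis as a mean exposure ratio, matching the planned analysis.

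Option 1 also needs clarity on the Section 8.3 rule that drops a patient whose predose concentration exceeds 5% of Cmax, which is worded without separating first-dose from steady-state days. With the 8 to 16 hour half-life in Section 1.1 and simple exponential decline, 24 hours leaves 2^(−24/8) = 12.5% to 2^(−24/16) = 35%. Applied to Days 28 and 63, the rule could therefore remove most patients from the proportion.

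The cost is wording, one extra summary with a wide interval and a little programming. No new samples or visits are needed.
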